- **If the repeat ALT and/or AST are >3 x ULN AND TB >1.5 x ULN at any time point**, the subject must be discontinued from study medication, the Sponsor notified and the end of treatment visit performed within 72 hours. At the end of treatment visit, medical history including details of risk factors for liver disease will be requested and additional blood sampling done, see Appendix I. The Investigator will follow the subject every 72 hours until the ALT and AST are ≤ 2 x ULN or until ALT and AST are back to the baseline levels*. The frequency of retesting can decrease to once a week or less if abnormalities stabilize and the patient is asymptomatic.
- **If the repeat ALT and/or AST >8 x ULN at any time point**, the subject must be discontinued from study medication, the Sponsor notified and the end of treatment visit performed within 72 hours. At the end of treatment visit, medical history including details of risk factors for liver disease will be requested and additional blood sampling done (if not already done), see Appendix I. The Investigator will follow the subject every 72 hours until the ALT and AST are ≤ 2 x ULN or until ALT and AST are back to the baseline levels*. The frequency of retesting can decrease to once a week or less if abnormalities stabilize and the patient is asymptomatic.

* unless there are specific reasons for the ALT and/or AST elevations e.g. liver cancer

Subjects who meet discontinuation criteria for lack of glycemic control at specified visits (See [Table 6](#)) will be scheduled for a repeated measurement within 3-5 days. If the repeated FPG value still meets the criteria for discontinuation, the subject should discontinue the investigational product. Otherwise investigational product may be resumed unless otherwise contraindicated.

Table 6 Discontinuation criteria for lack of glycemic control

Visit (Period C)	FPG
Weeks 4 and 6	> 240 mg/dL (13.3 mmol/L)
Week 8	> 220 mg/dL (12.3 mmol/L)
Week 10	> 200 mg/dL (11.2 mmol/L)

All randomised subjects who do not complete the treatment period (Period C) will complete the end of treatment visit (Week 12) study procedures as soon as possible but at the latest within 7 days after discontinuation of study drug. All randomised subjects will enter the 4-week follow-up period (Period D).

If a subject is withdrawn from study, see [Section 5.9](#).

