6.4.3 Recording of adverse events

Time period for collection of adverse events

All Adverse Events will be collected from the start of the Placebo lead-in Phase (Period B) throughout the treatment period including the Follow-up Phase (Period D). SAEs will be collected from the time when the informed consent is obtained until the Follow-up Phase.

Variables

The following variables will be collect for each AE;

- AE (verbatim)

- the date when the AE started and stopped
- maximum intensity
- whether the AE is serious or not
- investigator causality rating against the Investigational Product (yes or no)
- action taken with regard to investigational product
- outcome
- treatment required

In addition, the following variables will be collected for SAEs:

- Date AE met criteria for serious AE
- Date Investigator became aware of serious AE
- AE is serious due to
- Date of hospitalisation
- Date of discharge
- Probable cause of death
- Date of death
- Autopsy performed
- Causality assessment in relation to Study procedure(s)
- Causality assessment in relation to Other medication
- Description of AE

Maximum intensity will be graded according to the following definitions:

- mild (awareness of sign or symptom, but easily tolerated)
- moderate (discomfort sufficient to cause interference with normal activities)
- severe (incapacitating, with inability to perform normal activities)

- very severe (debilitating, significantly incapacitates patient despite symptomatic therapy)

It is important to distinguish between serious and severe AEs. Severity is a measure of intensity whereas seriousness is defined by the criteria in Section 6.4.2. An AE of severe intensity need not necessarily be considered serious. For example, nausea that persists for several hours may be considered severe nausea, but not an SAE. On the other hand, a stroke that results in only a limited degree of disability may be considered a mild stroke but would be an SAE.

The Investigator will assess causal relationship between Investigational Product and each Adverse Event, and answer “yes” or “no” to the question “Do you consider that there is a reasonable possibility that the event may have been caused by the investigational product?”

Causal relationship in cases where the disease under study has deteriorated due to lack of effect will be classified as no reasonable possibility.

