For SAEs causal relationship will also be assessed for other medication. Note that for SAEs that could be associated with any study procedure the causal relationship is implied as “yes”.

A guide to the interpretation of the causality question is found in Appendix B to the Clinical Study Protocol.

Adverse Events based on signs and symptoms

All AEs spontaneously reported by the patient or reported in response to the open question from the study personnel: “Have you had any health problems since the previous visit?” or revealed by observation will be collected and recorded in the CRF. When collecting AEs, the recording of diagnoses is preferred (when possible) to recording a list of signs and symptoms. However, if a diagnosis is known and there are other signs or symptoms that are not generally part of the diagnosis, the diagnosis and each sign or symptom will be recorded separately.

Adverse Events based on examinations and tests

Deterioration as compared to baseline in protocol-mandated laboratory values, vital signs and other safety variables will only be reported as AEs if they are clinically significant, fulfil any of the SAE criteria, are the reason for discontinuation of treatment with the investigational product, or require the patient to receive specific corrective therapy. If a deterioration in a laboratory value/vital sign is associated with clinical signs and symptoms, the sign/symptom will be reported as an AE and the associated laboratory result/vital sign will be considered as additional information. Any new or aggravated clinically relevant abnormal medical finding at a physical examination as compared with the baseline assessment will be reported as an AE.

Clinically relevant deterioration in non-protocol-mandated measurements will be reported as AE(s).

Wherever possible the reporting investigator uses the clinical, rather than the laboratory term (eg, anaemia versus low haemoglobin value).

Hypoglycaemic events

Signs and symptoms of hypoglycaemia, hypoglycaemia episodes, or discontinuation due to hypoglycaemia should not be reported on the AE eCRF page unless the event fulfils protocol criteria for a Serious Adverse Event (see Section 6.4.2), in which case an SAE must be reported in addition to the hypoglycaemic eCRF pages for hypoglycaemia. A separate section in the eCRF will be used to document all reported episodes of hypoglycaemia.

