The subject will be asked to always self-monitor fasting blood glucose in case of symptoms suggestive of hypoglycaemia and to register any signs of hypoglycaemia in the supplied subject's card.

A hypoglycaemic event can be either

- An episode with symptoms and confirmed low glucose.
- An episode with low glucose.
- An episode with symptoms when glucose was not measured.

For the evaluation of hypoglycaemic events special attention will be given to as described below.

- Major hypoglycaemic events, defined as symptomatic events requiring external assistance due to severe impairment in consciousness or behaviour, with a capillary or plasma glucose value <3.0 mmol/L (<54 mg/dL), and prompt recovery after glucose or glucagons administration.

- Minor hypoglycaemic event, defined as either a symptomatic event with a capillary or plasma glucose value <3.5 mmol/L (<63 mg/dL), and no need for external assistance, or an asymptomatic blood glucose measurement <3.5 mmol/L (<63 mg/dL).
- Events suggestive for hypoglycaemia, with symptoms that the subject experiences as hypoglycaemia and no confirmative measurement.

Data to be collected for each hypoglycaemic event:

- Date of start and stop and time of the day for start
- If symptoms are present or not and which symptoms
- If finger stick value obtained and the plasma glucose value
- Intervention needed for recovery, max intensity, action taken, causality and possible contributing factors
- Time of last drug administration
- Time of last meal

The subject's card will be reviewed and data regarding hypoglycaemic events transcribed into the eCRFs at each clinical visit. A new subject's card for the next period will be handed over to the subject. If a major hypoglycaemic event occurs, or more than one minor event since last visit, the subject should contact the investigator. For recording of hypoglycaemic events/symptoms suggestive of hypoglycaemic events as AEs, see Section 6.4.3.

Hyperglycemic events

Fasting plasma glucose(FPG) will be measured at each visit. For the visits which pre-specified glycemic parameters on FPG are established (See Table 6), subjects are checked whether they have lack of glycemic control/hyperglycemic events.

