12.2.2 Analysis of safety data

All safety data will be listed and summarised descriptively by treatment group.

The number and percentage of subjects who had any AEs, SAEs, AEs that lead to discontinuation, drug-related AEs and other significant AEs will be summarised.

Adverse events will be classified by body system and by preferred term using MedDRA. The number and percentage of subjects with AEs occurring after the first dosing date (including the first dosing date) by body system and by preferred term will be summarised. If necessary, similar summary will be made for SAEs and drug-related AEs.

For continuous safety variables, observed value and changes from baseline at each time point will be summarised using descriptive statistics. For categorical safety variables, the number of subjects in each category will be summarised at each time point.

All laboratory safety variables outside the reference range will be listed.

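### Stops for worsening FPG meet the laboratory AE rule while non-serious hypoglycaemia stops are kept off the AE page, so the descriptive counts of AEs and AE discontinuations can lean towards dapagliflozin

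*Protocol*

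**What the plan says.** Four parts of the protocol bear on this.

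- **Laboratory AE rule (6.4.3, the part on examinations and tests).** A worsening from baseline in a mandated laboratory value, vital sign or other safety variable counts as an AE only under certain triggers. Two are clinical significance and meeting an SAE criterion. The rule also covers changes that "are the reason for discontinuation of treatment with the investigational product, or require the patient to receive specific corrective therapy".
- **Stops for high FPG (5.8.1, 5.8.2, 6.4.9).** Lack of glycaemic control is study-specific criterion 11. Table 6 sets absolute FPG limits: above 240 mg/dL at Weeks 4 and 6, above 220 at Week 8 and above 200 at Week 10. Section 5.8.2 adds: "If the repeated FPG value still meets the criteria for discontinuation, the subject should discontinue the investigational product". FPG is measured at every visit. Section 6.4.9, under other safety assessments, says that at the Table 6 visits "subjects are checked whether they have lack of glycemic control/hyperglycemic events".
- **Stops for hypoglycaemia (6.4.3, Hypoglycaemic events).** Signs, episodes and "discontinuation due to hypoglycaemia should not be reported on the AE eCRF page unless the event fulfils protocol criteria for a Serious Adverse Event". All episodes go to a separate eCRF section, which under 6.4.9 records action taken and causality.
- **Analysis (12.2.2).** Counts and percentages by treatment group are planned for "subjects who had any AEs, SAEs, AEs that lead to discontinuation". There are also rows for events judged related to the drug and for other events of significance. The section does not say how either kind of glycaemic stop is handled.

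On causality, 6.4.3 adds: "Causal relationship in cases where the disease under study has deteriorated due to lack of effect will be classified as no reasonable possibility".

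**The concern.** The safety objective (2.4) is tolerability of each dose in reference to placebo, and the count of AEs leading to discontinuation is one of the main tables that answers it. A stop because glucose was not controlled is a failure of efficacy. If it is recorded as an AE discontinuation, the table partly measures efficacy, and placebo looks less well tolerated because it does not lower glucose. Glycaemic stops in the other direction, which would be expected on active drug if anywhere, are left out of the same count unless serious.

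The recording rule takes effect at data collection. If sites code identical stops differently, a later analysis plan can only partly repair the result.

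**Working it through.** **Step 1. Does a Table 6 stop meet the laboratory AE rule?** The rule has two conditions: worsening from baseline, and at least one trigger. A confirmed Table 6 value is a reason for stopping, so the trigger is met. Worsening depends on the subject. For efficacy variables, 11.1 sets baseline at pre-dose Week 0.

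- FPG 190 at Week 0 and 230 at Week 8, confirmed: above the 220 limit and above baseline. The rule is met.
- FPG 220 at Week 0 and 205 at Week 10, confirmed: above the 200 limit but below baseline. The subject stops, and the rule is not met.

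The second pattern is possible. The exclusion for FPG above 240 before randomisation applies only to subjects treated up to enrolment, and the Table 6 limits fall over time. So the rule catches those FPG stops that are also deteriorations, not all of them.

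**Step 2. Is there an exemption?** None for lack of glycaemic control. The causality sentence in 6.4.3 fixes the rating of lack-of-effect deterioration and does not say that such a case is not an AE. The next heading but one does contain an exemption, for hypoglycaemia only, with an SAE exception.

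**Step 3. Do the stop reasons settle the coding?** Section 5.8.1 lists adverse event (including laboratory abnormality) as one reason and lack of glycaemic control as another. It does not say whether they exclude each other, so both codings of the same stop are consistent with the text.

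**Step 4. Which way does it lean?** Section 1.4 reports that in the global Phase 2b study FPG fell in a dose-related way on dapagliflozin, and that hypoglycaemia AEs were more frequent on dapagliflozin than on placebo. It also reports no confirmed hypoglycaemia. More FPG stops are therefore expected on placebo, and few hypoglycaemia stops in any arm.

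**Step 5. How large could it be?** The plan states no figure to reproduce and gives no stop rates, so every rate below is an assumption. A subject stops once, so the rates add. Let *t* be other AE stops (equal in all arms), *gP* and *gD* FPG stops on placebo and on a dose, and *h* non-serious hypoglycaemia stops on a dose (none on placebo). The difference in AE-discontinuation rate, dose minus placebo, is:

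- as written: (*t* + *gD*) − (*t* + *gP*) = *gD* − *gP*
- both kinds counted: *gD* + *h* − *gP*
- neither counted: 0

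With 55 subjects per arm, and all FPG stops taken to be deteriorations and coded as AEs:

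| *gP* | *gD* | As written | Of 55 | Both counted, *h* = 2% | Neither |
|---|---|---|---|---|---|
| 2% | 2% | 0 points | 0.0 | +2 points | 0 |
| 5% | 2% | −3 points | 1.7 | −1 point | 0 |
| 10% | 2% | −8 points | 4.4 | −6 points | 0 |
| 15% | 0% | −15 points | 8.2 | −13 points | 0 |

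If only half of the FPG stops are deteriorations, the third row halves: 0.5 × (2% − 10%) = −4 points, or 2.2 of 55. Leaving hypoglycaemia out shifts the result by *h* alone, 0 to 2 points. Almost all of the lean therefore comes from the FPG side.

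**The case against.** The strongest reply is that the protocol already separates the reasons. Lack of glycaemic control has its own criterion, every discontinuing subject is asked the reason, and a site can record a Table 6 stop there without calling it an AE. The laboratory rule is also worded as a limit on reporting, and FPG appears among the efficacy laboratory variables (6.3.1.1), not in the standard safety panel (6.4.5). This shows that the favourable coding is open to sites. It does not show that it is required, and 6.4.9 places FPG-based hyperglycaemia under safety.

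Several stronger readings are tempting, and the documents do not support them:

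- *Every stop for high FPG becomes an AE.* It does not, because the rule needs worsening from baseline and Table 6 uses absolute limits.
- *Hypoglycaemia stops are barred from the AE page.* Those meeting the SAE criteria are reported there, and the rest stay visible on their own pages.
- *The trial would falsely show significantly fewer AE stops on dapagliflozin.* Section 12.2.2 plans descriptive summaries, with no test and no pooling of doses. Any such probability would rest on assumed rates and on an analysis that is not planned.
- *Drug-related AEs are distorted.* The causality convention rates lack-of-effect deterioration as not related, so that row is protected.

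It is also fair to say that AEs are tabulated by preferred term, so hyperglycaemia terms can be identified, and that a table of discontinuations by reason is often left to the analysis plan. Both help with display. Neither settles what a site enters on the AE page, which this protocol governs.

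**Conclusion.** The point holds in a limited form. Followed literally, 6.4.3 brings FPG stops with worsening from baseline into the AE count and leaves non-serious hypoglycaemia stops out. Section 5.8.1 leaves room for different coding of the same stop. The descriptive counts of any AE and of AEs leading to discontinuation can therefore lean towards dapagliflozin, and their meaning can vary by site.

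The size is unknown. The range of 0 to 15 percentage points in AE discontinuations rests on assumed FPG stops of 2% to 15% on placebo and 0% to 2% on a dose, equal other AE stops, and all FPG stops being coded as AEs. Fewer deteriorations or mixed coding would shrink it. In the any-AE row the effect is further diluted, because a subject who already has another AE adds nothing. The primary HbA1c analysis is untouched.

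**What to change.** In 6.4.3, beside the hypoglycaemia rule, state one coding rule for a stop under criterion 11 taken alone. Record it as discontinuation for lack of glycaemic control, and as an AE only if it is an SAE or has symptoms or a complication reportable in their own right. In 5.8.1, the two stop reasons should be read consistently with that rule.

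In 12.2.2, tabulate all discontinuations by arm and reason, with separate rows for AE, hypoglycaemia and lack of glycaemic control. If the current AE rule is kept, show any AE and AEs leading to discontinuation with and without hyperglycaemia terms.

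The cost is about two sentences and one extra table. The downside is a slightly lower AE count on placebo, so the doses look slightly less favourable by comparison. Table 6, the stopping criteria and clinical management stay as they are.

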6.4.4 Reporting of serious adverse events

Investigators and other centre personnel must inform appropriate AstraZeneca representatives via the web based data capture (WBDC) system of any SAE which occurs in the course of the study within one calendar day (i.e., immediately but no later than the end of the next business day) of when he or she becomes aware of it. Follow-up information on SAEs must also be reported by the Investigator within the same time frame.

The AstraZeneca representative will work with the Investigator to compile all the necessary information and ensure that Bristol-Myers Squibb receives a report by day one for all SAEs. All SAEs have to be reported, whether or not considered causally related to the investigational product or to the study procedure(s). SAEs will be recorded from the time of informed consent. SAE information will be entered and submitted into the WBDC system on the relevant eCRF modules.

If the system is unavailable, the Investigator should contact the AstraZeneca representative immediately recognising that the same reporting time frames still apply. The Investigator is responsible for completing the eCRF as soon as the system becomes available again. The

AstraZeneca representative will forward all information relevant to the SAE to Bristol-Myers Squibb Pharmacovigilance via email.

AstraZeneca will provide the information on the serious adverse drug reactions collected domestically and abroad regarding the investigational product to the Head of the study site, Investigators and the regulatory agency as per local requirements. The Head of the study site must submit a written report to the IRB providing the information reported by AstraZeneca.

6.4.5 Laboratory safety assessment

Standard clinical laboratory tests (Standard Safety Laboratory Panel) for safety assessment will be performed at:

- Enrolment visit
- Week -4 of the lead-in phase
- Week 0, 1, 2, 4, 6, 8, 10 and 12 of the double-blind treatment phase.
- Week 16 of the follow-up phase.

Blood and urine samples will be obtained at specified time points for laboratory evaluations (see [Table 1](#)). The central laboratory for this study will perform the analysis of all scheduled laboratory tests except for urine HCG pregnancy test and will provide reference ranges for these tests. All samples for clinical laboratory testing must be collected in the morning after the subject has fasted for at least 10 hours prior to collection.

The following laboratory variables will be measured:

Screening

- Hepatitis Screening Panel
 - Hepatitis A Viral Antibody IgM and IgG
 - Hepatitis B Viral Antibody IgM (anti-HBc)
 - Hepatitis C Virus Antibody (anti-HCV)
 - Hepatitis B Surface Antigen (HBsAg)
- Thyroid stimulation hormone (TSH)
- Prothrombin time (PT)
- Activated partial thromboplastin time (APTT)

Standard Safety Laboratory Panel:

Hematology

- Hemoglobin
- Hematocrit
- Red blood cell count indices
- White blood cell count and differential
- Platelet count

Serum chemistry

- Aspartate Aminotransferase (AST, SGOT)
- Alanine Aminotransferase (ALT, SGPT)
- Alkaline phosphatase (ALK-P)
- Creatine Kinase (Creatine Phosphokinase, CK, CPK)
- Total Bilirubin (TB)
- Blood Urea Nitrogen (BUN)
- Bicarbonate
- Serum Creatinine (Scr)
- Electrolytes – sodium, potassium, chloride, calcium, magnesium and phosphate
- Total Protein, Albumin
- Uric acid

Cystatine C

Markers of bone metabolism:

- Parathyroid hormone
- Osteocalcin
- 25-vitamin D

- C-terminal cross-linking telopeptides of type I collagen (CTX)
- Bone-specific alkaline phosphates
- Procollagen type-1 N-terminal propeptide (P1NP)

Urinalysis by dipstick

- pH, protein, glucose, leukocyte esterase, blood
- Microscopy if dipstick positive for blood or leukocyte esterase
- Urine HCG pregnancy test for WOCBP (HCG minimum sensitivity of 25 IU/L; performed at site)

If a urine HCG test is positive, a blood specimen will be obtained and a serum pregnancy test will be performed by the central laboratory for confirmation.

Spot Urine Collection

On the day of the collection the subject is to urinate in the toilet and flush away the first urine in morning, and collect the second urine in the clinic or hospital. The specimen is kept in a refrigerator.

The following laboratory parameters will be analyzed by a central laboratory. The results of glucose concentration from baseline and onwards will not be reported to subjects, the investigator and the sponsor. At Visit 1, only albumin (calculated albumin to creatinine ratio) will be measured.

- Glucose concentration(glucose mg/dL x g creatinine)
- Albumin (calculated albumin to creatinine ratio)
- Total protein (calculated protein to creatinine ratio)
- Urinary Sodium (calculated sodium to creatinine ratio)
- Creatinine (mg/dL)
- α 1-Microglobulin (mg/dL x g creatinine)
- N-acetyl glucosamine (NAG)
- Urine pH

24 hours Urine Collection

24 hour urine collection is done at Week 0 and Week 12 in subjects who give consent. 24 hour urine collection is allowed to be done on a separate day of the study visit if collected within 7 days before visit. On the day of the collection in the morning, the subject is to urinate in the toilet and flush away the first urine, and record the time. The subject will collect all urine day and night, including the urination on the next day up to the point 24-hours after the beginning of collection. The urine should be kept cool during the 24-hour period. After collecting the final urine, record the total urine volume. A portion of the 24 hour urine will be collected for a urine sample after fully mixing and uniforming the urine container. The urine sample should be given to the investigators within 2 hours after removing from cold storage.

The following laboratory parameters will be analyzed by the central laboratory.

- Glucose concentration
- Creatinine

Specimen Collection and Transport

The detailed methods for specimen collection, handling, processing, shipping, and storage will be supplied in the Investigator's Laboratory Manual provided by the Central Laboratory. All clinical laboratory tests will be performed by the Central Laboratory or designated reference laboratory.

For blood volume see Section [7.1](#)

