- c All randomized subjects not completing the treatment period should have Visit 13 procedures done as soon as possible but at the latest within 7 days after discontinuation of investigational products, and subsequently enter the 4-week follow-up period.
- d Glucose meter is provided to subjects and they check their blood glucose values if they have symptoms of hypoglycemia.
- e Call Registration Center to enroll subjects when informed consent is obtained at Visit 1, to randomize subjects at Visit 6, and when subject completes Period C or early discontinue Period C.
- f Subjects treated with anti-diabetic medication up to enrolment should have HbA1c ≤ 8% at Visit 1 to enter Period A, and the other type of subjects will enter Period B if HbA1c ≥ 7% but ≤ 10% at visit 1. All subjects should have HbA1c ≥ 7% but ≤ 10% at visit 5 to be randomized.
- g Subjects treated with anti-diabetic medication up to enrolment will be withdrawn if FPG > 240 mg/dL.
- h At Visit 6, OGTT is performed if FPG is <180 mg/dL at visit 5. At Visit 13, OGTT is not performed in subjects who did not perform OGTT at Visit 6, subjects who did not complete period C or subjects whose FPG is ≥ 180 mg/dL at Visit 12. At Visit 13, blood samples are drawn 60, 90, 120, 180 and 240 minutes after administration of 75 g oral glucose solution.
- i Plasma samples for analysis of dapagliflozin are obtained before administration of dapagliflozin at Visit 7, 10 and 12. At Visit 13 plasma samples are obtained at 60, 90, 120, 180 and 240 minutes after administration of dapagliflozin. If the subjects perform OGTT at Visit 13, plasma samples are obtained simultaneously with OGTT blood samples.
- j 24 hour urine collection is done in subjects who give consent. 24 hour urine is collected from the morning of the previous day to the visit up to the morning of the visit. 24 hour urine collection is allowed to be done on a separate day of the study visit if collected within 7 days before the visit. Subjects do not need to perform 24 hour urine collection at visit 6 if they do not meet HbA1c ≥ 7% but ≤ 10% at Visit 5. At Visit 13(Week 12), 24 hour urine is not performed in subjects who did not complete Period C

Clinical Study Protocol
Drug Substance Dapagliflozin
Study Code D1692C00005
Edition Number 1
Date

k Includes anti-HAV (IgM, IgG), HBsAg, and anti-HCV, and anti-HBc

Table 2 Visit design and time windows

Visit ID	Visit description	Visit window
Visit 1	Enrolment (Screening) ^a	-12 weeks

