6.2.4 Treatment period (Period C)

The following assessment will be performed at Period C.

- Inclusion and exclusion criteria (Week 0)
- Brief/Complete physical examination
- Vital signs, body weight
- Orthostatic blood pressure and orthostatic heart rate (Week 0, 2, 4 and 12)
- Waist circumference (Week 0 and 12)
- ECG (Week 0 and 12)
- Urine HCG pregnancy test for WOCBP (Week 0, 1, 6 and 12)
- Standard Safety Laboratory Panel (Blood and Urine)
- Post-prandial glucose, insulin, C-peptide during OGTT (Week 0 and 12, if applicable) (See Section [6.3.1.2](#))

- Urine glucose, creatinine and sodium concentrations during OGTT (Week 0 and 12, if applicable) (See Section 6.3.1.2)
- PK sample collection (Week 1, 6, 10 and 12)
- Spot urine sample (See Section 6.4.9) (Week 0, 6 and 12)
- Serum sample for markers of bone metabolism (Week 0, 8 and 12)
- 24 hour urine collection (Week 0 and 12) (See Section 6.4.5)
- HbA1c, FPG, fasting insulin, fasting C-peptide, fasting serum lipids (See Section Table 7)
- Cystatine C (Week 0 and Week 12)

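### When the 24-hour urine collection ends on the morning of Visit 6 or Visit 13, Protocol Section 6.4.5 tells the subject both to flush and to keep the first-morning void

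*Protocol*

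**What the plan says.** Four statements in the Protocol bear on the first urine passed on the morning of Visit 6 (Week 0) or Visit 13 (Week 12).

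- **Schedule.** Section 6.2.4 lists "Spot urine sample (See Section 6.4.9) (Week 0, 6 and 12") and "24 hour urine collection (Week 0 and 12) (See Section 6.4.5"); Table 1 agrees. Both samples are therefore due at Weeks 0 and 12. (The spot line points to Section 6.4.9, but the collection procedure is in Section 6.4.5.)
- **Spot urine, Section 6.4.5.** On the day of the spot sample the subject is to "flush away the first urine in morning, and collect the second urine in the clinic or hospital".
- **24-hour urine, Section 6.4.5.** The first urine on the starting morning is discarded and the time noted. After that, "The subject will collect all urine day and night, including the urination on the next day up to the point 24-hours after the beginning" of the collection.
- **Timing, Table 1 note j.** "24 hour urine is collected from the morning of the previous day to the visit up to the morning of the visit". As an alternative, Section 6.4.5 states that "24 hour urine collection is allowed to be done on a separate day of the study visit if collected within 7 days before visit".

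The 24-hour collection is made only by subjects who consent to it and, at Week 12, only by those who completed Period C. Its result feeds tertiary endpoint 2(f) in Section 2.3, the change from baseline in the 24-hour urinary glucose:creatinine ratio.

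**The concern.** On the default timing, the first void on the visit morning falls under two opposite rules: it is the void to be flushed before the spot sample, and it is also the urine that completes the 24-hour collection. No sentence ranks one rule above the other. The two paragraphs also use nearly the same flushing instruction for different mornings (the visit morning for the spot sample, the starting morning for the 24-hour sample), which makes a mix-up easier.

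At stake is the completeness of the 24-hour sample. A subject who flushes the void hands in a collection without its last portion, while one who keeps it, or who collected on a separate earlier day, hands in a full one. Handling could differ between subjects, or between one subject's Week 0 and Week 12, and in the second case the mismatch enters the change score directly. It would be hard to detect afterwards. Section 6.4.5 asks for the start time and the total volume, but not for a closing time or a note that the last void was included. Section 5.4.1 withholds urine glucose results from investigators and sponsor during Periods C and D, so an odd value would not prompt a query.

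**Working it through.** **Step 1: who meets the contradiction.** Four conditions must hold together.

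1. The subject consented to 24-hour collection.
2. The visit is Visit 6 or Visit 13. Spot urine is also taken at Visits 1, 10 and 14, but no 24-hour collection is due then.
3. The collection ends on the visit morning, as in note j. A collection on a separate day that ends before the visit morning raises no clash.
4. The first void of that morning falls within the 24 hours, so that the 24-hour text claims it.

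The documents do not say how many subjects this covers.

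**Step 2: what is lost.** If the spot instruction is followed, the 24-hour container lacks that one void. Anything passed during the night has already been collected under the day-and-night rule. If the 24-hour instruction is followed and the second void is given as the spot sample, nothing is lost, and the spot sample is still a second void.

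**Step 3: effect on the ratio.** The Protocol states no figure to reproduce. Let f be the share of the day's creatinine in the lost void, and r its glucose:creatinine ratio relative to the rest of the day (set to 1). The true 24-hour ratio is (1 - f) + f·r and the measured ratio is 1, so

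relative shift = 1 / (1 - f + f·r) - 1.

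The documents give neither f nor r. Assuming f from 0.15 to 0.35 and r from 0.4 to 1.3:

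| f | r = 0.4 | r = 0.7 | r = 1.0 | r = 1.3 |
|---|---|---|---|---|
| 0.15 | +9.9% | +4.7% | 0.0% | -4.3% |
| 0.25 | +17.6% | +8.1% | 0.0% | -7.0% |
| 0.35 | +26.6% | +11.7% | 0.0% | -9.5% |

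For example, f = 0.35 and r = 0.4 give 1 / (0.65 + 0.14) - 1 = 1 / 0.79 - 1 = +26.6%. With r = 1.3 the result is 1 / (0.65 + 0.455) - 1 = 1 / 1.105 - 1 = -9.5%.

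**Step 4: effect on the change score.** Write B and W for a subject's true ratios at Week 0 and Week 12, and e for the relative shift. If the void is lost at both visits with the same e, the measured change is (1 + e)(W - B), so the change is scaled by 1 + e. If it is lost only at Week 12, the measured change is (1 + e)W - B, with error e·W. If it is lost only at Week 0, the error is -e·B.

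**Step 5: where the endpoint is used.** Section 12.2.1.3 names the tertiary variables to be analysed by ANCOVA, and 2(f) is not among them. It falls under the descriptive summaries of continuous efficacy variables. HbA1c, FPG, the HbA1c response rate and the sample size do not depend on it.

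**The case against.** The case on the other side is substantial, and most of it limits the point without removing it.

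- **The clash can be avoided.** The separate-day option does that for those who use it. It is a permission, though, and the default in note j remains contradictory.
- **A sensible site would put the first void in the container.** The 24-hour text is the more specific of the two, and that order satisfies the aims of both samples. Loss is therefore possible, not certain. But the subject may well pass this void before arriving, with a plain instruction to flush it.
- **The Laboratory Manual may settle it.** Section 6.4.5 leaves detailed collection methods to that manual, which is not shown, so this cannot be excluded. The Protocol itself still gives both instructions.
- **A ratio partly cancels a lost void, and the instruction is the same in every arm.** Both are true. Cancellation is complete only at r = 1. Identical instructions make a difference in handling between arms unlikely, but by Step 4 a common proportional error still scales the absolute change and does not drop out.
- **Other urinary glucose data exist.** Glucose is also measured in spot urine and in urine collected during the OGTT. These are not 24-hour measures.

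A reader might infer that the whole overnight urine is lost as a rule at both visits, leaving a daytime ratio that is always too high. Assuming f of 0.25 to 0.40 and r of 0.3 to 0.7 would indeed give about +8% to +39%. The documents do not support this. Night-time voids are kept, the loss depends on which instruction is followed, and that range takes only r below 1, for which the Protocol offers no data.

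**Conclusion.** The contradiction is real but narrow. It concerns consenting subjects whose 24-hour collection ends on the morning of Visit 6 or Visit 13, and at Visit 13 only those who completed Period C. If they follow the spot instruction, the 24-hour sample lacks its last void, the recorded volume is short, and the ratio behind endpoint 2(f) may be biased. The range of -9.5% to +26.6% rests wholly on assumed values of f and r. It shows that the error need not be negligible and may go either way; it does not estimate the error. Handling that differs between subjects or visits is a further possible consequence. Because 2(f) is tertiary and descriptive, and the primary and secondary analyses are untouched, the severity is minor.

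**What to change.** Reconcile the two paragraphs of Section 6.4.5. State that when a 24-hour collection ends on the visit morning, the first void goes into the 24-hour container and closes the collection, and the next void, passed at the site, is the spot sample. Flushing the first void before the spot sample then applies only on mornings when no 24-hour collection is ending.

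The spot sample remains a second void, so its own rule is preserved. The cost is one sentence in the Protocol, with matching wording in the Laboratory Manual and subject instructions. It adds no sample and no visit.
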